6.2 Study Drug Formulations

Standardised recipes for pancakes and cookies will be given to participants. Recipes are clearly labelled and clear updosing instructions (including change of recipe) are given to subjects at commencement of OIT, and with reminders by the study team at updosing intervals. All ingredients will be weighed where possible. Standardised frying pans and scoops will be used for pancakes. Doses of egg protein consumed daily will be determined by the quantity of pancake/cookie consumed following the dosing Tables 5 and 6.

6.3 Study Drug Administration

Initial escalation phase and all dose increments during the pancake build-up phase will be administered in the Allergy Unit under medical supervision. Dose increments during the cookie build-up phase will be performed at home as previous studies have reported very low risks of severe allergic reactions. This will reduce the number of hospital visits required. All doses (pancake and cookie) must be taken for a minimum of 1 week before the next updosing.

6.3.1 In the event of a dose-related allergic reaction

In the event of an allergic reaction to a dose of immunotherapy within 2 hours of a dose, either at updosing in hospital or after a dose given at home, families will be instructed to follow their Allergy Action Plan, and to contact the study team.

Anaphylaxis reactions at home

- Where a child is having objective symptoms consistent with possible anaphylaxis (e.g. wheeze, persistent cough, difficulty breathing, stridor or marked swallowing difficulties), families will be instructed to administer the adrenaline auto-injector pen, contact the study team on the Emergency number and call 995 for the child to be brought to KKH Children's Emergency for further evaluation and admission

Following resolution of symptoms, the previous tolerated dose will be given the next possible day, under medical observation.

Persistent/ bothersome symptoms at home

- For persistent symptoms that last ≥ 3 days (within 2 hours of the immunotherapy dose) consisting of abdominal pain, rhinoconjunctivitis or skin symptoms (Table 8 Grade 1), the investigator should consider a dose reduction to the previous tolerated dose for at least 3 days or until symptoms have mostly resolved.
- In the event of other symptoms that prove bothersome to the child, the dose can be reduced at investigator's discretion.
- In cases of dose reduction due to persistent/ bothersome symptoms, the original dose should be resumed once symptoms are deemed to have mostly resolved. *Upon resumption of original dose, subjects should be on the dose for at least 1 week before the next updosing.*
- For recurrent symptoms where dose reduction has not on its own been effective, the investigator may elect to offer participants an oral second-generation antihistamine, prior to OIT dosing, to reduce allergic symptoms to immunotherapy doses. If started, the use of these medications should be minimized, and then discontinued at the earliest opportunity. Antihistamines should not be taken on the day of updosing.

Mild symptoms at home

- For mild skin symptoms, itchy mouth, rhinoconjunctivitis or mild abdominal symptoms (Table 8 Grade 1), reassurance to families will be provided and the current dose will be continued, with contact with the study team as needed.

6.3.2 In the event of omitted doses

- If 1-2 days of immunotherapy is missed, the subject can continue with the current dose at home with the next scheduled updose to proceed as planned
- If 3-7 days of immunotherapy are missed,

- for pancake build-up phase - the previous dose will be given until the subject can attend the Allergy unit for repeat updosing. *Upon resumption of original dose, subjects should be on the dose for at least 1 week before the next updosing.*
- for cookie build-up phase - the previous dose will be given for a week before repeat updosing at home. *Upon resumption of original dose, subjects should be on the dose for at least 1 week before the next updosing.*

• If more than 7 days of immunotherapy are missed, dosing should stop until the subject can attend the Allergy unit for repeat updosing of the previous dose.

6.3.3 In the event of sick days

Families will be requested to contact the study team in the event of an intercurrent illness, to discuss reducing the dose depending on symptoms and intensity.

In the event of subject having an intercurrent illness, the investigator may pre-emptively reduce the OIT to the previous dose for the duration of the illness. *Upon resumption of original dose, subjects should be on the dose for at least 1 week before the next updosing.*

6.3.4 In the event of dose reduction for other reasons

Subjects are expected to be compliant to doses and will be encouraged to adhere to the protocol. In the event the subject is unable to take the current dose for reasons other than allergic reactions and sick days (eg. refusal from taste fatigue), the previous dose will be given until the original dose is resumed. *Upon resumption of original dose, subjects should be on the dose for at least 1 week before the next updosing.* If the subject is taking less than the previous dose, subsequent dosing will be managed as per omitted doses (Section 6.3.2).

6.4 Specific Restrictions / Requirements

Subjects in the control arm will be advised strict egg avoidance including all baked egg products. However for those who were already previously tolerating baked egg products, they will be allowed to continue consumption of baked egg products outside of study, up to a maximum of 2.5g baked egg protein (approximately equivalent to a slice of cake or one muffin) per week.

Subjects in the BER group undergoing cookie OIT will be counselled for strict egg avoidance including all baked egg products outside of the study treatment. Subjects in the BET group who had tolerated baked egg products prior to study will be allowed to continue the consumption of baked egg products outside of study, up to a maximum of 2.5g baked egg protein (approximately equivalent to a slice of cake or one muffin) per week. This limit is placed because baked egg consumption in BET subjects may enhance desensitisation to cooked egg, and subjects taking larger quantities of baked egg outside of pancake OIT may have better rates of desensitisation. However, as pancake OIT outcomes should be assessed

in a real-world setting, this will include allowing baked egg consumption in egg allergic children who are already tolerating baked egg.

Subjects who are receiving anti-IgE therapy, oral immunosuppressants, beta-blocker, ACE inhibitor or immunotherapy for other allergens will fall under the study's exclusion criteria and be withdrawn from study.

Subjects will be advised to avoid intense physical exercise up to 2 hours before and after each OIT dose intake.

6.5 **Blinding**

This is an open label study. Blinding will not be performed.

6.6 **Concomitant therapy**

Participants may continue usual medications, including those taken for asthma, rhinitis, and eczema during the study. Antihistamines must not be taken on the day of updosing and must be stopped prior to FC visits as per Section 4.3.2.8. Participants (or their parents) will be asked to document any use of medication (including rescue medication) in home diary cards.

All medications (prescription and over the counter) taken by the participant should be documented.

7 **SAFETY MEASUREMENTS**

7.1 **Definitions**

An adverse event (AE) is any untoward medical occurrence in a patient or clinical investigation subject administered a pharmaceutical product and which does not necessarily have a causal relationship with this treatment.

A serious adverse event (SAE) or reaction is any untoward medical occurrence that at any dose:

- results in or contributes to death
- is life-threatening
- requires inpatient hospitalisation or prolongation of existing hospitalisation
- results in or contributes to persistent or significant disability/incapacity or
- results in or contributes to a congenital anomaly/birth defect
- results in such other events as may be prescribed

Important Notes Relating to Definition of SAE:

- Hospitalisation refers to the requirement for overnight admission to hospital. Observation in hospital following an allergic reaction that is not immediately life threatening does not constitute a hospital admission.

- A subject who experiences an anaphylaxis reaction (e.g. hoarse voice, cough, wheeze, stridor not requiring intubation, transient hypotension) is not at “immediate risk of death” and such events will not be classified as SAE unless they fulfil SAE criteria.

The following criteria will constitute an SAE:

- Anaphylaxis occurring at in-hospital challenge *requiring more than two doses* of intramuscular adrenaline
- Anaphylaxis occurring in response to a dose of OIT outside the hospital environment, *requiring more than one dose* of intramuscular adrenaline.
- Clinician-confirmed diagnosis of eosinophilic oesophagitis (with positive histology).

7.2 Causality

The adverse event can be described as ‘**expected**’ if it caused symptoms and/or signs that could be reasonably described as a consequence of an allergic reaction to allergen exposure within the protocol. Symptoms of an allergic reaction are defined as any described within this protocol. An adverse event is considered “**unexpected**” when its nature or severity is not consistent with the investigator’s protocol.

An adverse event is defined as “**related**” when it has resulted from the administration of any of the research procedures. Related adverse events are defined as “**adverse reactions**”. All episodes of anaphylaxis occurring in response to a dose of OIT will be treated as an **AE of interest**.

In this study, the following may be used as a guide to aid consistency in classification of the relationship to study treatment. The descriptors outlined below are not intended to be prescriptive and the Site Investigator should classify each event according to the specific circumstances involved.

Probably related:

- Objective signs of an IgE mediated allergic reaction (hives, angioedema, vomiting, anaphylaxis) occurring within 1 hour of the study treatment in the absence of other known allergic triggers for that subject; AND
- Symptoms **cannot** be reasonably explained by subject’s clinical state, environmental or toxic factors or other treatments taken by the participant.

Possibly related:

- Objective signs of an IgE mediated allergic reaction (hives, angioedema, vomiting, anaphylaxis) occurring more than 1 hour but less than 4 hours after taking the study treatment; AND
- Symptoms **cannot** be reasonably explained by subject’s clinical state, environmental toxic factors or other treatments taken by the participant.

Unlikely to be related:

- Allergic symptoms occurring more than 4 hours after taking study treatment; or
- Symptoms **can** be reasonably explained by the subjects’ clinical state, environmental or toxic factor or other therapies taken by the participant. e.g. exacerbation of asthma or eczema; or
- Symptoms do not follow a known pattern of response for the study treatment.

Unrelated:

- Any event where an alternate cause is identified – e.g. allergic reaction following exposure to another food allergen in a subject with known allergy to that allergen; or
- The AE does not meet the criteria for the other categories above.

Not assessable:

- There is insufficient or incomplete evidence to make a clinical judgement of the causal relationship.

7.3 Collecting, Recording and Reporting of Adverse Events and Serious Adverse Events to CIRB

All adverse events will be recorded on a subject's diary from the time the participant provides consent until the time the event resolves or until 30 days after the participant completes study treatment. Adverse events may be discovered through observing and questioning the participant or receiving an unsolicited complaint and questioning the participant in an objective manner. All adverse events will be recorded, regardless of their severity or relation to study medication or procedures.

Reporting of adverse events involves the PI submitting to the approving CIRB the completed SAE Reporting Form within the stipulated timeframe. PI is responsible for informing the institution representative (local SAE resulting in death), sponsor or regulatory bodies as required and appropriate.

Reporting timeline to CIRB:

- SAE that result in death, regardless of causality, should be reported immediately - within 24 hours of the PI becoming aware of the event.
- All "related" SAE (definitely / probably / possibly) irrespective of severity or expectedness, need to be reported to CIRB within 24 hours of the PI becoming aware of the event.

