1.2.2 Rationale for Study Design

This is a randomised controlled study exploring the efficacy, safety and feasibility of a novel form of egg OIT using pancakes to induce desensitisation and sustained unresponsiveness in egg allergic patients. The control group receiving current standard care of egg avoidance, will be used to control for the incidence of natural resolution of egg allergy over the study period. Safety of OIT and its impact on quality of life measures will also be compared against the risk of accidental reactions among controls who continue strict egg avoidance. Allocation ratio of 2:1 (active:control) allows for more patients to be given a chance to receive OIT.

This is an open label study as we wish to assess a pragmatic approach to OIT with home preparation of pancakes and cookies using store bought eggs, in which blinding will not be feasible nor practical.

Subjects randomised to the active arm will undergo an open baked egg food challenge (FC) to determine their baseline baked egg tolerance. Baked egg tolerant (BET) patients will directly undergo OIT using pancakes. Baked egg reactive (BER) patients will commence OIT with baked egg (cookies), to first achieve desensitisation to baked egg before transitioning to pancakes. Desensitisation will be assessed by an open cooked egg FC at the end of treatment while SU will be assessed by an open cooked egg FC after stopping OIT for approximately 6 weeks.

Updosings for cookies will be done at home under the guidance of the study team based on the safety profile of other home-based baked egg OIT protocols (7),(8). Updosings for pancakes will be performed in the hospital as this has not been evaluated previously.

Subjects randomised to the control arm will continue strict egg avoidance and undergo an open cooked egg FC between 12 and 18 months.

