2.4.1 Potential Risks

Allergic reactions are expected during baseline challenges to cooked egg and baked egg and they also frequently occur through the course of OIT. The risk of experiencing an allergic reaction is higher in those undergoing OIT than those who are avoiding the allergen (9). Most adverse events are expected to be mild and local reactions (itch in mouth, rashes, abdominal pain or nausea). However, systemic reactions including anaphylaxis can occur, either in the hospital during FC/ updosings or with home doses.

It has been reported that small number of patients (~2%) undergoing OIT can develop eosinophilic oesophagitis (EoE), which is almost always reversible by stopping OIT, without long-term sequelae.

Risks from venepuncture are low and mainly associated with transient discomfort which can be mitigated by the use of local anaesthetics.

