4.3 Study Visits and Procedures Overview

There will be 9-10 hospital visits for the BET group, 10-11 hospital visits for the BER group over the entire study duration. There will be 2 hospital visits for the control group.

[figure not shown]

Figure 2: POET Study Timeline

Study Timepoints	TS	T0	T1C		T1P/ T2P		T3	T4
	Screening & Cooked Egg FC	Baked Egg FC	Cookie Initial Escalation	Home Cookie Build-up	Pancake Initial Escalation	Hospital Pancake Build-up	Exit Cooked Egg FC	SU FC
Informed consent	X							
Medical history	X							
Concomitant medications	X	X	X		X	X	X	X
Adverse events		X	X	X	X	X	X	X
Physical exam	X	X	X		X	X	X	X
Spirometry		(X)					(X)	
Asthma control test	X	(X)					(X)	
SCORAD	X							
POEM	X							
Skin Prick Test	X*						X	X
Blood test	X*						X	X
HRQL Assessments	X		X		X		X	X

Table 1: Study Procedures

(X) may be performed, depending on clinical need; X* - Results from SPT/ IgE performed within 3 months prior will be used and need not be repeated

X are procedures applicable to control subjects

FC – Food Challenge; SU – Sustained Unresponsiveness

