4.3.2.7 Sustained Unresponsiveness (SU) Food Challenge (T4)

Desensitised subjects in the active arm (tolerating 4443mg of cooked egg at T3) will be asked to stop OIT and all baked egg products (if they had been taking them) for approximately 6-8 weeks prior to returning for a repeat FC to assess for sustained unresponsiveness. The dosing protocol for SU FC will be the same as that of DS FC (Table 7).

Participants who tolerate 4443mg of cooked egg at SU FC will be allowed ad libitum cooked egg consumption post study. Participants who develop allergic reactions at SU FC will resume previous maintenance dose.

4.3.2.8 Clinical assessment and procedures during open FC (screening FC, baked egg FC, DS FC, SU FC)

All challenges will be conducted in the Allergy outpatient unit, with staff fully trained in the management of allergic reactions including anaphylaxis. Emergency equipment (including oxygen and suction) and medication will be checked beforehand, as per local protocol and international criteria for performance of FC.

All subjects will be assessed prior to FC to determine suitability for a challenge, as follows:

- No intercurrent illness
- No exacerbation in allergic symptoms (eczema, asthma, food allergy) in the preceding week.
- No short-acting β 2 agonists used in the past 12 hours
- No recent antihistamine exposure (e.g. cetirizine, loratadine) in the past 48 hours (72 hours for fexofenadine, 5 days for long-acting antihistamine (e.g. chlorphenamine, desloratadine).

- No oral steroids have been taken in the past 2 weeks
- Baseline observations (temperature, blood pressure, heart and respiratory rate, oxygen saturations,) within the normal range.
- Baseline physical examination must not reveal any significant acute findings.

The clinical team may elect to secure intravenous access by cannulation as an additional safety precaution at challenge. This will allow treatment to be easily and rapidly administered in the event of a significant allergic reaction, and also allows blood to be collected without further venepuncture.

Participants will be monitored including heart rate, blood pressure and oxygen saturations. Clinical manifestations will be assessed throughout the challenge.

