7.5 Safety Monitoring Plan

The PI will perform regular data and safety monitoring. Safety data including side effects and adverse reactions will be monitored from time of enrolment to completion of study. The PI will report AE/ SAE to CIRB as per guidelines stipulated above.

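### Sections 7.3, 7.5 and Table 1 give different AE collection windows: the 7.3 diary rule closes 12-26 days before T4 and has no defined end for controls

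*Combined protocol and SAP*

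**What the plan says.** **Start and end of recording.** Section 7.3: "All adverse events will be recorded on a subject's diary from the time the participant provides consent", continuing "until the time the event resolves or until 30 days after the participant completes study treatment".

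**Timing of T4.** Section 4.3.2.7: desensitised children in the active arm "will be asked to stop OIT and all baked egg products (if they had been taking them) for approximately 6-8 weeks" before the repeat challenge. Section 4 gives the same interval. Section 1.2.2 gives only the lower figure: "SU will be assessed by an open cooked egg FC after stopping OIT for approximately 6 weeks". Section 9.2.2 also uses 6 weeks.

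**Schedule of procedures.** In Table 1 (section 4.3) the "Adverse events" row is empty at TS and marked in the other seven columns, T0 through T4.

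**Safety monitoring.** Section 7.5: safety data are "monitored from time of enrolment to completion of study". Section 4.3.3 makes T4 the final visit for children desensitised at T3, and T3 the final visit for controls and for active children who are not desensitised.

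**Screening challenge.** It is part of TS (section 4.3.1), and consent comes before screening (section 12.1). Section 2.4.1: "Allergic reactions are expected during baseline challenges to cooked egg and baked egg".

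**Use of the data.** Safety is a secondary objective (section 2.3). Section 9.2.2 compares AE incidence between active and control groups with Fisher's exact test.

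**The concern.** The passages that define when AEs are collected do not agree. Site staff who follow 7.3 would stop the diary about a month after the last OIT dose. Staff who follow Table 1 or 7.5 would carry on to T4. In controls 7.3 has nothing to count from.

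The trial plans 33 children, and section 1.2.2 sets the safety of OIT against accidental reactions in controls. With so few children, a handful of events recorded under one rule and missed under another could change that comparison. The interval affected also matters in itself: it is when desensitised children have stopped daily egg exposure and protection may be fading, which is what T4 is meant to test.

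**Working it through.** The plan states no figure for this point, so there is none to reproduce. The check is date arithmetic and a side-by-side reading.

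**1. Gap between the 7.3 cut-off and T4.** Inputs: 30 days (7.3); 6-8 weeks from stopping OIT to T4 (4.3.2.7). Assumption: study treatment is completed when OIT stops after T3. Section 7.2 supports this, since it uses study treatment to mean the dose taken.

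Gap = weeks × 7 − 30.
- 6 weeks: 42 − 30 = 12 days.
- 8 weeks: 56 − 30 = 26 days.

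T4 is outside the 7.3 window across the whole stated interval. If the 6 weeks of 1.2.2 and 9.2.2 governs, the gap is 12 days.

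**2. Children affected.** Inputs: 22 active children, 65% desensitised, 30% attrition (section 9.1).
- 65% of all 22: 22 × 0.65 = 14.3.
- If attrition comes first: 22 × 0.70 × 0.65 = 10.0.

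So about 10 to 14 children would reach T4. No control does. Time outside the 7.3 window runs from 10 × 12 = 120 to 14.3 × 26 ≈ 372 child-days.

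**3. Which passage covers what.**

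| Period or visit | 7.3 | Table 1 | 7.5 |
|---|---|---|---|
| TS challenge | inside (from consent) | blank | starts at enrolment |
| Last 12-26 days off OIT | outside | no visit | inside |
| T4 challenge | outside | marked | inside |
| End point for controls | undefined | T3 is last visit | end of study |

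Each challenge is inside at least one rule and outside another. The late off-OIT interval is the weakest row: 7.5 covers it in principle, but no visit falls there, and the monthly calls in 4.3.2.4 belong to the cookie phase.

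**4. The recording tool.** Section 7.3 relies on a diary from consent. Section 4.3.2.5 hands out the daily dosing diary only after initial escalation, and its list for controls contains no diary. Section 6.6 asks participants to note medication use, including rescue medication, on home diary cards, but does not say when these are issued or for how long, and they record medication, not events.

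**5. The word *or* in 7.3.** The sentence joins follow-up of an existing event to resolution with a 30-day limit on recording, and does not say which applies to new events.

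**The case against.** The strongest reply is that nothing of consequence is lost.

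- **T4.** An AE entry is scheduled in Table 1. Section 4.3.2.8 has symptoms assessed before each dose and the outcome and eliciting dose entered in the participant record. Failing T4 is itself the sustained-unresponsiveness outcome.
- **SAEs.** The 30-day limit sits in the sentence about the diary. SAE reporting is a separate paragraph, timed from the investigator's awareness. Section 7.1 names severe anaphylaxis at an in-hospital challenge as an SAE, and 7.2 counts events caused by research procedures as related.
- **TS.** 7.3 starts at consent, which precedes the challenge. A positive screening challenge is an eligibility route that comes before randomisation, so it says nothing about OIT.

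All of this stands. A reader might infer that reactions at the first and last challenges, or an SAE at T4, fall outside the safety record, or might count the children expected to react at T4 as lost events. The documents do not support that. It would mean taking 7.3 over Table 1 at T4 and then Table 1 over 7.3 at TS, and expected T4 failures are recorded outcomes.

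The reply does not remove three things: the date conflict, the missing end point for controls, and the late off-OIT interval. Questioning at T4 could recover some events from that interval, but by recall, and the protocol does not ask for it specifically.

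**Conclusion.** The point holds as an internal contradiction in the AE collection window, worth correcting because AE incidence is compared between arms. The 7.3 window closes 12-26 days before T4, affecting about 10 to 14 active children under the planning assumptions. It has no defined end for controls, and Table 1 disagrees with 7.3 at TS.

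The practical exposure is narrow: accidental reactions outside visits in those 12-26 days. The documents give no rate for such reactions, so the number of events at risk cannot be estimated.

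The date arithmetic rests on reading study treatment as OIT ending at T3. If the sponsor meant it to run through T4, 7.3 should say so, and the gap for controls would remain. The text available does not show which Table 1 entries apply to controls, so nothing here depends on that marking.

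**What to change.** - **One window, in the same terms in 7.3, 7.5 and Table 1, for both arms:** from consent to the final study visit (T3 or T4 as set in 4.3.3). For active children who withdraw early, to 30 days after the last OIT dose taken in the study; for controls who withdraw, name an end point such as the date of withdrawal.
- **Do not tie the general end point to the last OIT dose.** Under 4.3.2.7, children who react at T4 go back on their maintenance dose, so such a window might never close.
- **Separate** the window for new events from follow-up of events still open when it ends.
- **Continue the diary** through the off-OIT interval, and use the same recording method in controls.
- **Mark AEs at TS** in Table 1.
- **In 9.2.2,** analyse the pre-randomisation screening-challenge reactions apart from the between-arm comparison. Only active children have a T3-T4 interval, so also say whether events in it enter that comparison.

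**Cost.** Amendment wording, one table cell, 6-8 more weeks of diary use for children who reach T4, a diary for controls if they do not already have one, and slightly more AE recording. One trade-off: for active children whose last visit is T3, 7.3 may now run up to 30 days past that visit. Ending at T3 gives that up; keeping it would need the same follow-up in controls. No dose, challenge or treatment rule changes.
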